5.4.2 Secondary Efficacy Assessments

- Signs and Symptoms: ACR20/ACR50/70 over time
- Remission and change from baseline: DAS28-CRP, DAS-ESR, SDAI, CDAI, Boolean over time
- PK: predose concentration (C_{trough}) of BMS-986142 at time-points specified in [Table 5.5.1-1](#)
- MRI assessment of change from baseline in synovitis, osteitis (bone marrow edema), bone erosion and cartilage loss (joint space narrowing) in hands/wrists at timepoints specified in [Table 5.1-2](#)

[REDACTED]

5.4.4 **Imaging Assessments**

Any incidental findings of potential clinical relevance on chest x-ray or any additional imaging performed that are not directly associated with the objectives of the protocol should be evaluated and handled by the Study Investigator as per standard medical/clinical judgment. Images will be submitted to imaging core lab for central analysis. Assessment of hand and wrist MRI by Investigator is not expected.

5.4.4.1 **MRI Assessment**

MRI scanners used in the study must be deemed qualified by BMS/assigned Imaging Core Lab prior to subject scans. The hand/wrist that is clinically most swollen at Screening Visit will be imaged using a whole body MRI system. Of note, the Screening Visit MRI is considered the baseline MRI assessment for this study. The SAME hand/wrist that was imaged at Screening will be imaged at Week 4, and Week 12 on the SAME MRI scanner as was used at screening. The Screening Visit MRI is to be performed approximately 14 days prior to randomization. Week 4 and Week 12 MRIs are to be performed \pm 7 days of the scheduled Week 4 visit and Week 12 visit, respectively. **Subjects who terminate the study early require an MRI at the early termination (ET) visit only if ET < 4 weeks or > 8 weeks from date of randomization and should have their early termination (ET) MRI NO MORE than 7 days from their Early Termination (ET) Visit.**

Sites should schedule two MRI appointments with radiology department 7 days apart in the event that a MRI exam needs to be repeated due to technical difficulties. Technical issues with MRI identified at the investigator site or Imaging Core Lab should be re-imaged within 7 days of notification.

Subjects with severe renal insufficiency (ie, estimated glomerular filtration rate (eGFR) or GFR < 30 mL/min/1.73m²), will be excluded from the study, as they are at increased risk of

Nephrogenic Systemic Fibrosis, a rare, but serious, condition associated with the use of gadolinium-based MRI contrast agents.

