7 STATISTICAL ANALYSES

7.1 General Methods

The table below provides an overview of the efficacy analyses to be performed.

Table 1: Planned Efficacy Analyses

Measure of Interest (Primary and Secondary Efficacy Endpoints):	Analysis Method
Co-primary endpoints: ACR20 and 70 response rate at Day 85	Chi-Square test, two sided p-value will be provided. Point estimates and 95% CI of treatment difference.
Binary endpoints : ACR20, ACR50 and ACR70 response rate over time from baseline to Day 85; DAS28-CRP<2.6, DAS28-ESR<2.6, CDAI<=2.8, SDAI<=3.3 and Boolean remission over time from baseline to Day 85	Point estimate and 95% CI of response rate, point estimates and 95% CI of treatment difference.
Continuous endpoints: DAS28-CRP, DAS28-ESR, CDAI, SDAI, MRI scores (synovitis, osteitis, bone erosion and cartilage loss)	Mixed model analysis, point estimates and 95% CI for mean change from baseline within treatment groups, point estimates and 95% CI for mean change from baseline between treatment groups.

The Chi-square tests will be used to compare the ACR20 and ACR70 response rates at Day 85 between each of the active treatment arms and the placebo arm. The Chi-square p-value will be provided for each comparison between the active treatment and the placebo arm. Within each treatment group, the statistical testing will be performed for ACR20 at level of 0.05 first. If it is statistically significant, then the statistical testing will be performed for ACR70. Otherwise, testing will be stopped for this treatment group. All treatment groups will follow the same testing procedure. In addition, the difference of the response rates between each active treatment and the placebo will be estimated and their corresponding 95% confidence interval will be calculated. All subjects who discontinue prematurely during the treatment period or receive prohibited medications (refer to [Section 8.3](#)) will be counted as non-responder at subsequent visits.

For each of the binary endpoints, the estimate and its corresponding 95% confidence interval will be calculated for the difference of the proportions between each active treatment arm and the placebo arm at the specified visit, similar to the primary analysis except no p-values will be provided.

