7.5.2 Secondary Efficacy Endpoints in Double-blind Period

For each of the binary endpoints (DAS28-CRP<2.6, CDAI<=2.8 etc.), the estimate and its corresponding 95% confidence interval will be calculated for the difference of the proportions

between each active treatment arm and the placebo arm for each applicable visit, similar to the primary analysis except no p-values will be provided.

For each of the continuous endpoints (DAS28-CRP, CDAI, etc.), the mixed effect model will be fit with treatment and visit as the fixed effects and measurements within each subject as the repeated measurements. The baseline value will be added into the model as a covariate if necessary. Based on the mixed effect model, the estimate and 95% confidence interval will be calculated for the difference between each active treatment and the placebo at each specified visit. No p-values will be provided. In addition, descriptive summary statistics of mean change from baseline and 95% confidence interval for each treatment arm will be provided. The missing data in continuous measures will be handled via utilization of mixed model procedure in SAS.

7.5.2.1 *Magnetic Resonance Imaging (MRI)*

Magnetic resonance imaging will be performed at baseline, Week 4 and Week 12 (or at the time of discontinuation, e.g., early termination visit [ET]). The independent read of MRI image data will be performed by two primary readers who have no knowledge of the subject's identity, treatment arm or time point chronologic sequence. The readers will be presented with the image set(s) of the most clinically swollen hand/wrist acquired at baseline and of that same hand/wrist acquired at Week 4 and Week 12 for the assessment of four parameters of bone erosion, bone marrow edema (osteitis), synovitis, and cartilage loss (joint space narrowing). The scoring of four parameters will be assessed according to the OMERACT RAMRIS criteria⁹.

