The MRI score for each parameter is the sum of scores at joints/bone ends where applicable by each reader. The MRI score that is used in the analyses is calculated as the average of MRI scores provided by the two readers for each parameter per each subject at each visit. If a MRI score from one of the readers is missing, then MRI score from the other reader will be used. If the score is missing for both readers at any given time point, the average score is considered missing. If a case requires adjudication, a consensus read of all four parameters will be performed by the two readers working together as defined in the charter. The consensus score will be used in the analysis in this case for each of the four parameters.

If there are more than 20% of joints/bone ends with missing score, the MRI score of each parameter will be considered missing. If there are less than or equal to 20% of joints/bone ends with missing score, the MRI score of each parameter from the missing joints/bone ends will be carried forward from previous scan (e.g., baseline to Week 4, Week 4 to Week 12), or carried backward from later time point or early termination visit (ET) scan if previous scan is not available (e.g., Week 12 to Week 4). If subjects had missing complete MRI assessment at Week 4 or 12, their assessment will be imputed via linear in/extrapolation. Imputation will require a subject to have available scores at minimum 2 visits (including baseline, Week 4, Week 12 or early termination (ET) visit). Subjects with no baseline or only baseline scores will be excluded from the analysis.

The following analyses will be performed based on imputed data unless specified otherwise. In addition, the analysis of changes from baseline may be performed based on as-observed data to assess the robustness of results at the presence of missing data.

The summary of changes from baseline to Week 4 and 12 in each of four parameters will be provided by treatment group using a mixed model. The proportion of subjects with new erosion count (defined as erosion score =0 at baseline and erosion score >0 at post baseline) per hand/wrist will be also summarized at Week 4 and 12.

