8.5 Missing Measurements

8.5.1 *Imputation of Missing Data for Binary Variables*

This imputation is applicable for all binary variables (ACR20/50/70, DAS28-CRP <2.6, DAS28-ESR <2.6, and remission status defined by CDAI, SDAI and Boolean definition).

If the response cannot be assessed due to missing data or a subject's early discontinuation, the following conventions will be implemented in a sequence:

- Any subject who prematurely discontinues the trial during the double-blind period after receiving study medication will have data imputed as non-responder at all scheduled protocol visits subsequent to the point of discontinuation up to the end of the double-blind period.
- After any imputation above or none, if for some reason the binary variable still can't be determined, including the case where baseline data is missing, then its value will be set to non-responder.

For listings, missing responses will be presented as missing.

8.5.2 *Imputation of Missing Data for Continuous Variables*

For the analysis of changes from baseline values (e.g., individual components of ACR, DAS28-CRP, and DAS28-ESR etc), missing values will be dealt with via the longitudinal repeated measures analysis assuming MAR (missingness at random).

For all safety (including laboratory measurements), and PK measures, missing values will not be imputed.

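### A wholly missing Week 12 MRI is filled by linear extrapolation, which scales the Week 4 change by about 2.3 to 3 and is not reconciled with the SAP's own mixed-model rule

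*SAP*

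**What the plan says.** SAP 7.5.2.1 deals with a scan that is missing altogether: "If subjects had missing complete MRI assessment at Week 4 or 12, their assessment will be imputed via linear in/extrapolation". The entry condition is low: "Imputation will require a subject to have available scores at minimum 2 visits (including baseline, Week 4, Week 12 or early termination (ET) visit"). Baseline plus one later scan is therefore enough. The filled data are the default: "The following analyses will be performed based on imputed data unless specified otherwise". The alternative is optional and limited to one type of analysis: "the analysis of changes from baseline may be performed based on as-observed data to assess the robustness of results".

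Elsewhere the SAP takes a different route. Table 1 (SAP 7.1) lists "MRI scores (synovitis, osteitis, bone erosion and cartilage loss") among the continuous endpoints analysed by mixed model. SAP 7.5.2 states: "The missing data in continuous measures will be handled via utilization of mixed model procedure in SAS". SAP 8.5.2 says that for changes from baseline "missing values will be dealt with via the longitudinal repeated measures analysis assuming MAR (missingness at random"). It separates out only safety and PK measures, and MRI is not named as an exception.

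Protocol 5.4.4.1 decides who has a late scan. Subjects who stop early "require an MRI at the early termination (ET) visit only if ET < 4 weeks or > 8 weeks" from randomisation. The same section makes the Screening scan, taken about 14 days before randomisation, the baseline MRI. SAP Table 4 instead lists the MRI baseline at Day 1, with MRI windows of Days 15-57 for Week 4 and Days 58-113 for Week 12.

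**The concern.** A subject who leaves between Weeks 4 and 8 is not required to have an early-termination (ET) scan. If that subject has a Week 4 scan, the Week 12 score is a straight line drawn through baseline and Week 4 and carried forward eight weeks. Any error in the Week 4 change is scaled up with it, and the result enters the analysis as though it had been read from an image. The plan gives no reason to expect synovitis or osteitis to change linearly over 12 weeks.

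At stake are the Week 12 changes in the four RAMRIS scores, which are secondary endpoints, and the MRI responder proportions built on the same filled data. For the responder proportions, the rule works against the rest of the plan: SAP 8.5.1 counts a drop-out as a non-responder on the binary endpoints it lists, whereas here a drop-out can be projected into a responder.

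**Working it through.** The documents give no power or precision figure for MRI, so there is none to reproduce.

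**Inputs from the documents.** Target Days 29 and 85 and the MRI windows (SAP Table 4); baseline scan about 14 days before randomisation, scans within 7 days of the visit, and the ET-scan rule (Protocol 5.4.4.1); the smallest detectable change (SDC) with two readers (SAP 7.5.2.1); 82 subjects per arm (Protocol 8.1), a planning figure only, since the Protocol synopsis says recruitment stops early.

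**Assumed, not in the documents.** Share of Week 12 scans filled, f = 10% (20% as an alternative); r = true Week 4 change divided by true Week 12 change, from 1/3 (linear from Day 1) to 1 (plateau by Week 4); equal SDs of change at both visits; Week 4/Week 12 correlation 0.5 to 0.7.

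**1. Multiplier.** k = (days from baseline to Day 85) / (days from baseline to last scan).

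| Last scan | Baseline at Day 1 | Baseline 14 days earlier |
|---|---|---|
| Day 29 | 84/28 = 3.0 | 98/42 = 2.33 |
| Day 22 | 84/21 = 4.0 | 98/35 = 2.8 |
| Day 36 | 84/35 = 2.4 | 98/49 = 2.0 |
| ET, Day 15 | 84/14 = 6.0 | 98/28 = 3.5 |

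If derived visits are used throughout, a Day 15 scan falls in the Week 4 window and k is 3.0. The SAP does not choose among these time axes. ET scans from Day 58 fall in the Week 12 window and need no extrapolation.

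**2. Noise.** The variance of a filled change is k² times that of the observed change: 9 at k = 3, and 5.4 at k = 2.33. Relative to complete data, the SE ratio is √(1 - f + f·k²). At f = 0.10 this is √1.80 = 1.34 (k = 3) or √1.444 = 1.20 (k = 2.33).

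**3. Responder cut-off.** A responder has a change below -SDC. The SAP formula makes the SDC 1.96 times the error SD of the two-reader average. With no true change, the chance of passing is Φ(-1.96/k): 2.5% for an observed scan, Φ(-0.84) = 20.0% at k = 2.33, and Φ(-0.653) = 25.7% at k = 3.

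**4. Floor.** Taking the summed scores as non-negative, a Week 4 fall of more than 1/k (33% at k = 3, 43% at k = 2.33) projects below 0. No floor is stated.

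**5. Bias in an arm mean**, as a share of the true Week 12 change, is f(k·r - 1). At f = 0.10:

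| r | k = 2.33 | k = 3 |
|---|---|---|
| 1/3 | -2% | 0% |
| 0.7 | +6% | +11% |
| 1 | +13% | +20% |

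At f = 0.20 each figure doubles.

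**6. Against the mixed model.** A simulation used 4,000 runs, 82 per arm, a true difference of -0.5 SD, and drop-out after Week 4 that is missing at random. With complete data the SE would be √(2/82) = 0.156.
- Likelihood estimate under missing at random: bias within 0.01; SD of the estimated difference 0.16 to 0.17 at 10 to 20% missing.
- Extrapolation at k = 3: SD 0.21 to 0.22 at 10% missing and 0.26 at 20%.
- Extrapolation under linear change (r = 1/3), with 20% missing on placebo and 10% on active: the difference is overstated by about 0.08 at k = 3 and 0.04 to 0.05 at k = 2.33.

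**The case against.** Several points on the other side stand.

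- A reader might infer that the SAP contradicts itself. The documents do not go that far. The MRI subsection sits under the general rule of SAP 7.5.2 and can be read as a specific exception, and the examples in SAP 8.5.2 do not include MRI. What is missing is a statement that it is an exception, and a reason for one.
- A reader might also infer that every affected change is multiplied by 3 or more. That needs a Day 1 baseline and a last scan no later than Day 29. With the Screening scan as baseline and actual dates, a Week 4 scan gives 2.0 to 2.8. The factor of 6 also needs an actual ET date combined with a Day 1 baseline.
- Nor is upward bias inevitable. It is near zero or slightly negative under linear change with equal drop-out. The larger figures need early plateau, for which the plan gives no support, least of all for erosion and cartilage loss.
- The group is limited. Those leaving after Week 8 should have a usable ET scan, and Protocol 5.4.4.1 provides for repeat imaging within 7 days after technical failure.
- MRI is secondary, carries no p-values (SAP 7.5, 7.5.2), and an as-observed analysis is already named.

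These points reduce the size of the concern without removing it. The variance inflation and the responder distortion do not depend on non-linearity, and the as-observed check is optional and does not cover the responder proportions.

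**Conclusion.** The point holds in a bounded form. SAP 7.5.2.1 makes single linear extrapolation the default for a missing Week 12 MRI, does not reconcile it with the mixed-model rule that on its face covers MRI, and leaves the time axis and the floor undefined. Two programmers could obtain factors of 2.3 and 3.0 for the same Week 4 scan.

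The firm consequences are a 5.4- to 9-fold error variance for each filled change and, with no true change, a 20 to 26% chance of passing the responder cut-off instead of 2.5%. The bias in the mean, from about -2% to +20% at 10% missing with equal drop-out, depends on the assumed share missing and on the unknown time course. Differential drop-out can add bias even when change is linear. The co-primary ACR analyses are unaffected, and it would be wrong to conclude that the MRI results must favour the drug.

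**What to change.** In the SAP, before unblinding:

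1. Make the as-observed mixed model under missing at random the main analysis of MRI change from baseline, with ET scans assigned to visits by the MRI windows of Table 4.
2. Keep linear extrapolation only as a labelled sensitivity analysis. State whether it uses actual or nominal days, which day counts as baseline, and a floor at 0.
3. Do not derive MRI responder status from extrapolated scores. Treat a missing status as non-response, in line with SAP 8.5.1.
4. Cross-refer SAP 7.5.2.1 and 8.5.2 so that the rule for MRI is stated once. Interpolating a missing Week 4 score between two scans may stay, since it does not project beyond the data.

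No new data are needed. The cost is that subjects whose only post-baseline scan precedes Day 15 leave the main MRI analysis, whereas the present rule keeps them. That is a small loss of information on early drop-outs, and the sensitivity analysis would still include them.

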3.2 Secondary Objectives

- Assess additional efficacy outcomes of BMS-986142 at Week 12 and over 12 weeks of treatment as measured by ACR20, ACR50 and ACR70 response rates, DAS28-CRP change from baseline, DAS28-ESR change from baseline, Clinical Disease Activity Index (CDAI), Simplified Disease Index (SDAI), and Boolean remission.
- Assess the safety and tolerability of BMS-986142.
- Evaluate Ctrough of BMS-986142.
- Assess the efficacy of BMS-986142 + MTX to MTX alone in reducing synovitis, osteitis, bone erosion and cartilage loss in hands/wrists by MRI at Weeks 4, and 12, from baseline.

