The construction of confidence intervals for binary variables will be based on normal approximation, if the number of the events in each individual treatment arm is at least 5. Otherwise, confidence interval using an exact method will be provided. The exact confidence intervals for binary variable within treatment group and between treatment groups will be constructed.

For each of the continuous endpoints, the mixed effect model will be fit with treatment and visit as the fixed effects and measurements within each subject as the repeated measurements. The baseline value will be added into the model as a covariate if necessary. Based on the mixed effect model, the estimate and 95% confidence interval will be calculated for the difference between each active treatment and the placebo at each specified visit.

The results will be presented by treatment groups unless otherwise specified.

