7.5 Efficacy

The efficacy analyses will be performed using the efficacy analysis population. The results will be grouped by “as randomized” treatment groups, unless otherwise specified. No formal statistical testing was pre-specified for other efficacy endpoints except the primary endpoint of ACR20 and ACR70 response at Day 85. The analyses of binary endpoints and continuous endpoints will be provided over time including the milestone visits (e.g. Day 85).

Note: If the enrollment is terminated for all treatment arms based on Week 4 interim analysis, the sensitivity analyses, per-protocol analyses, sub-group analyses and additional analyses as defined in the following sections may not be performed based on smaller sample size.

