In addition, the proportion of responders who show no progression of damage based on each of four parameters will be summarized by treatment group at Week 4 and 12 using point estimate and 95% CI, and point estimate and 95% CI of the difference in proportions between the treatment groups. The responder at Week 4 and 12 is defined as the change score from baseline is less than negative value of the smallest detectable change (SDC)¹⁰. The SDC is calculated by $1.96 \times SD_{\Delta(\text{change-scores})}/(\sqrt{2} \times \sqrt{k})$ in which $SD_{\Delta(\text{change-scores})}/\sqrt{2}$ represents the measurement error of single change-scores and k=2 represents the number of readings or raters used for the actual analyses of the trial. The calculation of SDC will be based on the data from two readers excluding the cases that require adjudication.

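### The MRI proportion that the SAP labels as no progression is defined by a rule that counts only improvement beyond measurement error

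*SAP*

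**What the plan says.** SAP section 7.5.2.1 (Magnetic Resonance Imaging) plans, beyond the mixed-model analysis of RAMRIS change, a summary in which "the proportion of responders who show no progression of damage based on each of four parameters will be summarized by treatment group" at Weeks 4 and 12, with 95% confidence intervals for each arm's proportion and for the between-arm difference. The next sentence sets the rule: a responder is "defined as the change score from baseline is less than negative value of the smallest detectable change".

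The SDC is 1.96 × SD(Δ change scores) / (√2 × √k). The SAP explains that SD/√2 "represents the measurement error of single change-scores and k=2 represents the number of readings or raters used".

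Two other places fix the direction of the scores. The same section describes new erosion as "defined as erosion score =0 at baseline and erosion score >0 at post baseline", so a rise is damage. SAP section 3.2 states the MRI objective as "reducing synovitis, osteitis, bone erosion and cartilage loss in hands/wrists by MRI", so benefit is a fall. Neither document gives a +SDC threshold or any other definition of non-progression.

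**The concern.** The label and the rule describe different groups. With higher scores worse, and change taken as follow-up minus baseline, a change below -SDC is a fall larger than reader error, which is improvement. Not progressing is a wider condition that also covers subjects who stayed the same within measurement error. The SAP does not call those subjects progressors, but it leaves them out of a proportion that carries the no-progression name.

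Followed as written, the report would show an improvement rate under a no-progression heading, for four parameters at two visits, with arm differences and intervals. A reader would take it as a statement about how many subjects were protected from structural damage, which it is not.

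**Working it through.** The documents give no planned rate, power or effect size for this proportion, so there is no stated figure to reproduce. The check has three parts.

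**1. A case that needs no assumption.** A subject has an erosion score of 0 at baseline and 0 at Week 12. There is no progression and the change is 0. Because the score cannot go below 0, this subject can never have a change below -SDC and so can never be counted.

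**2. What the SDC formula implies.** Let σ be the SD of the error in one reader's change score.

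- The difference between two readers' change scores has SD √2 × σ.
- With k = 2, SDC = 1.96 × √2σ / (√2 × √2) = 1.386σ.
- The analysed score is the mean of two readers, whose change has error SD σ/√2 = 0.707σ.
- SDC / error SD = 1.386 / 0.707 = 1.96.

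The formula is therefore coherent for a two-reader mean. For a subject with no true change and normal error:

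- P(change < -SDC) = Φ(-1.96) = 2.5%
- P(change ≤ +SDC) = Φ(1.96) = 97.5%

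The 95% of such subjects within ±SDC separate the two readings. At the planned 82 per arm, 2.5% is 82 × 0.025 = 2.05 expected events, and the binomial chance of fewer than 5 is 94.5%. In that situation the SAP section 7.1 condition for intervals "based on normal approximation, if the number of the events in each individual treatment arm is at least 5" would usually fail and the exact method would apply.

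**3. Illustrative rates when true change varies.** The documents give no expected MRI change or reader SD, so these inputs are assumptions, in units of σ. Let true change have mean m (positive is worsening) and SD s. The total SD is t = √(s² + 0.5). Then P(change < -SDC) = Φ((-1.386 - m)/t) and P(change ≤ +SDC) = Φ((1.386 - m)/t).

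| m | s | t | change < -SDC | change ≤ +SDC |
|---|---|---|---|---|
| 0 | 0 | 0.707 | 2.5% | 97.5% |
| 0 | 0.7 | 0.995 | 8.2% | 91.8% |
| 0.2 | 0.5 | 0.866 | 3.4% | 91.5% |
| 0.5 | 0.7 | 0.995 | 2.9% | 81.3% |
| -0.5 | 0.7 | 0.995 | 18.7% | 97.1% |
| -1.0 | 0.7 | 0.995 | 34.9% | 99.2% |

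Active minus placebo, with s = 0.7 in both arms:

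- Placebo worsens by 0.5, active stable on average: 8.2 - 2.9 = +5.3 points under the written rule; 91.8 - 81.3 = +10.5 points under ≤ +SDC.
- Placebo stable on average, active improves by 1.0: 34.9 - 8.2 = +26.7 points under the written rule; 99.2 - 91.8 = +7.4 points under ≤ +SDC.

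Neither of these two readings always gives the larger difference.

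**The case against.** The strongest reply is that the rule is explicit and can be programmed, and that everyone who meets it has indeed not progressed. On that view only the name is loose. The word responder and the objective of reducing the scores suggest that improvement was meant, at least for synovitis and osteitis. This may well be so, and renaming would then be enough. But the label suits erosion and cartilage loss, and the documents do not settle which half is the slip. A rate that omits every stable subject is not a no-progression rate, whatever the intention.

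A second reply is that +SDC is only one possible threshold. That is correct. Reading no progression as change ≤ 0 gives 50% for a subject with no true change, and arm differences of +19.2 and +34.3 points in the two scenarios above. This changes the size of the gap but not the mismatch, and it is a further reason to state the definition.

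Third, the sparse-count remark holds only near zero true change. With m = 0 and s = 0.7 the rate is 8.2%, about 6.7 expected events among 82, and the chance of fewer than 5 is about 19%. The exact method already covers sparse counts, so this is not a separate harm. The model is also idealised: some scores come from one reader, consensus or imputation, and the scores are bounded at zero.

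Finally, reversing the sign of change does not rescue the text. With baseline minus follow-up, the rule would select detectable worsening, which conflicts with the label even more.

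**Conclusion.** The concern holds: the label and the rule in SAP section 7.5.2.1 cannot both stand. As written, the analysis reports improvement beyond SDC under a no-progression name. With no true change, the gap is 2.5% against 97.5% if no progression means change ≤ +SDC; this rests on normal error and two-reader mean scores. The other rates and arm differences are illustrative.

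The consequence is limited. This summary is not among the secondary endpoints in SAP section 4.2 and has no entry of its own in Table 1. SAP section 7.5 says "No formal statistical testing was pre-specified for other efficacy endpoints except the primary endpoint" of ACR20 and ACR70. The co-primary comparisons, sample size, mixed-model RAMRIS change and new-erosion summary are unaffected. It should still be corrected, because the label would mislead a reader of the report and the possible definitions can give materially different results.

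**What to change.** Before unblinding, state for each of the four parameters which quantity is meant. The simplest course is to report two proportions: no progression, as change ≤ +SDC, and improvement beyond SDC, as change < -SDC. If another threshold for no progression is preferred, such as change ≤ 0, write it down. If only improvement was intended, keep the rule and rename the endpoint. It would also help to state that change is follow-up minus baseline.

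The cost is one or two lines of SAP text and one line of code, with no new reads or data.
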